### **7.6.2 Serious Adverse Event Reporting**

Investigators and the protocol sponsor must conform to the adverse event reporting timelines, formats and requirements of the various entities to which they are responsible, but at a minimum those events that must be reported within 5 or 10 days of PI notification are those that are:

- related to study participation,
- unexpected, and
- Harmful or have the potential to cause harm

The study clinician will complete a SAE Form within the following timelines:

- All deaths and immediately life-threatening events, related and unrelated, will be recorded on the SAE Form and submitted within 24 hours of site awareness.
- Other SAEs will be submitted within 72 hours of site awareness.

This information should be reported to the PI and to the DSMC. All SAEs will be followed until satisfactory resolution or until the site investigator deems the event to be chronic or the adherence to be stable. Other supporting documentation of the event may be requested and should be provided as soon as possible.

As a follow-up to the initial report, within the following 48 hours of awareness of the event, the investigator shall provide further information, as applicable, on the unanticipated event or the unanticipated problem in the form of a written narrative. This should include a copy of the completed Unanticipated Problem form, and any other diagnostic information that will assist the understanding of the event. Significant new information on ongoing unanticipated adverse effects shall be provided promptly.

Adverse events that do not fit the above immediately reportable criteria must still be reported to the IRB at each annual review, either in a summary or tabular format.

### **7.6.3 Unanticipated Problem Reporting**

Incidents or events that meet the OHRP criteria for UPs require the creation and completion of an UP report form. It is the site investigator's responsibility to report UPs to their IRB and to the Data Coordinating Center (DCC)/study sponsor. The UP report will include the following information:

CONFIDENTIAL

This material is the property of the NYU School of Medicine and Langone Medical Center. Do not disclose or use except as authorized in writing by the study sponsor

- Protocol identifying information: protocol title and number, PI's name, and the IRB project number;
- A detailed description of the event, incident, experience, or outcome;
- An explanation of the basis for determining that the event, incident, experience, or outcome represents an UP;
- A description of any changes to the protocol or other corrective actions that have been taken or are proposed in response to the UP.

To satisfy the requirement for prompt reporting, UPs will be reported using the following timeline:

- UPs that are SAEs will be reported to the IRB 5 or 10 days of the investigator or the study team becoming aware of the event. Unexpected death of unknown causality and any event requiring immediate intervention to prevent subject harm requires 5 calendar days.
- Any other UP will be reported to the IRB within 5 or 10 days of the investigator or the study team becoming aware of the problem.
- All UPs should be reported to appropriate institutional officials (as required by an institution's written reporting procedures), the supporting agency head (or designee), and OHRP within 5 or 10 days of the IRB's receipt of the report of the problem from the investigator and the study team.

#### **7.6.4 Reportable Events**

The reportable events noted above will be reported to the IRB using the form: "Reportable Event Form" or as a written report of the event (including a description of the event with information regarding its fulfillment of the above criteria, follow-up/resolution and need for revision to consent form and/or other study documentation). Copies of each report and documentation of IRB notification and receipt will be kept in the Clinical Investigator's study file. The Principal Investigator is responsible for reporting all unexpected problems involving risk to participants or others to NYULH Perlmutter Cancer Center CTO.

#### **7.6.5 Reporting Procedures – Notifying the Study Sponsor and Perlmutter Cancer Center**

The following describes events that must be reported to the study sponsor and Perlmutter Cancer Center in an expedited fashion. Any member of the study team who becomes aware of an event informs the rest of the study team staff and the PI/Sub-I. The PI/Sub-I determines if the event is unexpected and related to the trial and if the event is harmful to the subject.

The study team member will complete a NYULH CTO Medical Events Form within the following timelines in an expedited fashion:

##### **Initial Report: within 24 hours:**

- All deaths and immediately life-threatening events, whether related or unrelated, will be recorded on the NYULH CTO Medical Events Form and submitted to the DCC/study sponsor within 24 hours of site awareness.
- All report forms must be signed and dated by the Principal Investigator. If the Principal Investigator is not available at the time of the initial report, then the form can be submitted by a Sub-Investigator. This form should be reviewed by the Principal Investigator, whom sign/date initial report upon return.

Report to: [[contact]](mailto:[contact])

AND

Principal Investigator

[name]

Associate Professor at NYU Grossman School of Medicine Department of Anesthesiology, Perioperative Care and Pain Medicine

[name]

[[contact]](mailto:[contact])

CONFIDENTIAL

This material is the property of the NYU School of Medicine and Langone Medical Center. Do not disclose or use except as authorized in writing by the study sponsor

AND

PCC Medical Monitor

**Follow-up report: within 48 hours:**

As a follow-up to the initial report, within the following 48 hours of awareness of the event, the investigator shall provide further information, as applicable, on the unanticipated event or the unanticipated problem in the form of a written narrative. This should include a copy of the completed Unanticipated Problem form, and any other diagnostic information that will assist the understanding of the event. Significant new information on ongoing unanticipated adverse effects shall be provided promptly to the study sponsor.

**Other Reportable events:**

- **Deviations from the study protocol**

Any protocol deviations initiated without Sponsor and the investigator's IRB approval that may affect the scientific soundness of the study, or affect the rights, safety, or welfare of study subjects, must be reported to the Sponsor and to the investigator's IRB as soon as a possible, but **no later than 5 or 10 days** of the protocol deviation.

- **Withdrawal of IRB approval**

An investigator shall report to the sponsor a withdrawal of approval by the investigator's reviewing IRB as soon as a possible, but no later than **10 days** of the IRB notification of withdrawal of approval.

### **7.6.6 Reporting Procedures – Notifying the IRB**

Federal regulations require timely reporting by investigators to the NYULH IRB of unanticipated problems posing risks to subjects or others. The following describes the NYULH IRB reporting requirements, though Investigators at participating sites are responsible for meeting the specific requirements of their IRB of record.

This section also specifies the NYULH IRB requirements for investigator reporting of unanticipated problems posing risk to subjects or others, including adverse events. The IRB requirements reflect the current guidance documents released by the Office of Human Research Protections (OHRP), and the Food and Drug Administration (FDA) and are respectively entitled "Guidance on Reviewing and Reporting Unanticipated Problems Involving Risks to Subjects or Others and Adverse Events" and "Guidance for Clinical Investigators, Sponsors, and IRBs: Adverse Event Reporting – improving Human Subject Protection".

The NYULH IRB address is:

NYULH School of Medicine IRB  
[name]  
[name]

**Report Promptly, but no later than 5 or 10 days:**

Researchers are required to submit reports of the following problems promptly but no later than 5 or 10 days from the time the investigator becomes aware of the event:

**Unanticipated problems including adverse events that are unexpected and related**

- Unexpected: An event is "unexpected" when its specificity and severity are not accurately reflected in the protocol-related documents, such as the IRB-approved research protocol, any applicable investigator brochure, and the current IRB- approved informed consent document and other relevant sources of information, such as product labeling and package inserts.
- Related to the research procedures: An event is related to the research procedures if in the opinion of the principal investigator or sponsor, the event was more likely than not to be caused by the research procedures.

CONFIDENTIAL

This material is the property of the NYU School of Medicine and Langone Medical Center. Do not disclose or use except as authorized in writing by the study sponsor

- Harmful: either caused harm to subjects or others, or placed them at increased risk

#### **Other Reportable events:**

The following events also require prompt reporting to the IRB, though no later than 5 or 10 days:

- **Complaint of a research subject** when the complaint indicates unexpected risks or the complaint cannot be resolved by the research team.
- **Protocol deviations or violations** (includes intentional and accidental/unintentional deviations from the IRB approved protocol) for any of the following situations:
  - one or more participants were placed at increased risk of harm the event has the potential to occur again
  - the deviation was necessary to protect a subject from immediate harm
- **Breach of confidentiality**
- **Incarceration of a participant** when the research was not previously approved under Subpart C and the investigator believes it is in the best interest of the subject to remain on the study.
- **New Information indicating a change to the risks or potential benefits** of the research, in terms of severity or frequency. (e.g. analysis indicates lower-than-expected response rate or a more severe or frequent side effect; Other research finds arm of study has no therapeutic value; FDA labeling change or withdrawal from market)

#### **Reporting Process**

The reportable events noted above will be reported to the IRB using the form: "Reportable Event Form" or as a written report of the event (including a description of the event with information regarding its fulfillment of the above criteria, follow-up/resolution and need for revision to consent form and/or other study documentation). The contact information for submitting safety reports is noted below:

Email: [[contact]](mailto:[contact])

AND

Principal Investigator

[name]

Associate Professor at NYU Grossman School of Medicine Department of Anesthesiology, Perioperative Care and Pain Medicine

[name]

[contact]

AND

PCC Assigned Medical Monitor

Copies of each report and documentation of IRB notification and receipt will be kept in the Clinical Investigator's study file.

#### **7.7 Study Halting Rules**

There are no predefined stopping rules.

### **8 Clinical Monitoring**

Clinical site monitoring is conducted to ensure that the rights and well-being of human subjects are protected, that the reported trial data are accurate, complete, and verifiable, and that the conduct of the trial is in compliance with the currently approved protocol/amendment(s), with GCP, and with applicable regulatory requirement(s). The completeness, accuracy and consistency of the data, and adherence to ICH Good Clinical Practice guidelines will be followed.

CONFIDENTIAL

This material is the property of the NYU School of Medicine and Langone Medical Center. Do not disclose or use except as authorized in writing by the study sponsor

## 9 Data Safety Monitoring

The PI and the Perlmutter Cancer Center Data Safety Monitoring Committee (DSMC) will be responsible for conducting systematic and periodic reviews of aggregate data and adverse events in accordance with the data safety monitoring plan. The PI and DSMC are responsible for overall data safety monitoring of the study.

The trial will be monitored for all adverse events, such as adverse medical symptoms to the study drug, and serious adverse events, such as an adverse study drug-related events every 6 months by the DSMC. The PI will also review these adverse effects once a month.

The following adverse effects will be monitored:

- Allergic reaction thought to be related to study drug
- Uncontrolled hypertension, hypotension, or arrhythmia thought to be related to study drug
- Severe psychomimetic side effects
- Severe respiratory event in PACU (such as reintubation, laryngospasm, or bronchospasm)

At the NYULH Perlmutter Cancer Center, all investigator-initiated protocols are subject to a standardized data and safety monitoring, which includes scientific peer review, IRB review and DSMC review as well as internal auditing.

The review of unanticipated problems and trial conduct for this trial occurs at several levels:

(1) Principal Investigator: Unanticipated problems are evaluated regularly by the principal investigator in conjunction with the research nurses, data manager and research team. In addition, serious adverse events are monitored for this study on a monthly basis by the research team.

(2) DSMC, semi-annually.

(3) Institutional Review Board (IRB): An annual report to the IRB is submitted by the trial PI for continuation of the protocol. It includes a summary of all unanticipated problems, total enrollment with demographics, protocol violations, and current status of subjects as well as available research data.

(4) In addition, the quality assurance unit will monitor this trial every 3 months, to verify adherence to the protocol; the completeness, accuracy and consistency of the data; and adherence to ICH Good Clinical Practice guidelines. The quality assurance unit's specialist will send an email notification of upcoming monitoring visit at least 2 weeks prior to each visit. The regulatory binder may also be requested for review. Monitoring visit reports are issued after each visit (usually within 24 hours of last day of monitoring).

## 10 Statistical Considerations

The primary outcome will be assessed with the BPI pain subscale at 24h postoperatively. We hypothesize subjects who received ketamine will have lower scores than those who received placebo. Secondary outcomes include changes in BPI (pain and interference subscales), PROMIS fatigue, PROMIS sleep, QoR-15, and BCPQ.

Descriptive statistics will be used to summarize continuous variables with mean and standard deviation, or categorical variables with frequency and percentage. The normality of the distributions for continuous variables will be tested using Q-Q plots and Shapiro-Wilk tests. If they are skewed, they will also be summarized using median and the inter-quartile range. A two-sided p-value<0.05 will be considered statistically significant. All analyses will be conducted using SAS 9.4 (SAS Institute Inc., Cary, NC).

CONFIDENTIAL

This material is the property of the NYU School of Medicine and Langone Medical Center. Do not disclose or use except as authorized in writing by the study sponsor

### **10.1 Statistical and Analytical Plans (SAP)**

Descriptive statistics will be used to summarize the demographic and baseline characteristics, with mean and standard deviation for continuous variable, or frequency and percentage for categorical variables. If continuous variables are skewed, the median and inter-quartile range will be used as well. To test differences in the demographic and baseline characteristics between the two arms, clinical variables that are continuous will be compared using Wilcoxon's rank-sum test, and those categorical variables will be compared using the Fisher's exact test. The baseline balance will be determined by following both statistical and clinical significance criterion, with the latter as the primary.

The primary endpoints are the BPI pain subscale at 24 and 48 hours. The difference between ketamine and placebo will be compared using Wilcoxon's rank-sum test. A mixed-model repeated measures (MMRM) approach will be used to assess differences of repeated measures for the BPI pain subscales at 24h and 48h between two treatment regimes. The MMRM model will include the baseline pain subscale, factors for treatment, time, and treatment by time interaction. Unbalanced baseline variables will also be included. SAS PROC MIXED will be used to perform the analysis. Model-based least square means will be obtained for difference between two treatment arms at each time point.

Secondary endpoints include scales for postoperative pain, mood, fatigue/sleep, and recovery. The difference of secondary outcomes between ketamine and placebo will be compared using Wilcoxon's rank-sum test. In addition, for outcomes with single occasion (such as PHQ-2 and GAD-2 scales) linear regression models will be utilized to quantify the effects of the ketamine treatment against the control while controlling for their preoperative value and unbalanced baseline variables. Their model-adjusted pairwise differences will be quantified using point estimates associated with 95% confidence intervals. Outcome variables that are obtained on more than one occasion (such as BPI, opioid use and fatigue scales at 1+1, 2+2, and 7+2 days after surgery) will also be analyzed with an MMRM approach to assess differences between two treatment regimes. The MMRM model will include factors for treatment, time, treatment-by-time interaction, their preoperative values and unbalanced baseline variables.

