**Enrollment/Baseline Visit (Visit 1, Day 0)**

- Obtain informed consent of potential participant verified by signature on written informed consent or electronic consent.
- Verify inclusion/exclusion criteria.
- Subjects will complete the questionnaire packet for baseline assessments which will include BPI, PROMIS sleep disturbance, PROMIS fatigue, PHQ-2, and GAD-2. This will be done either in-person, over the phone or electronically via REDCap link sent to subject.

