## 19 Schedule of Events

STUDY ASSESSMENTS & PROCEDURES	Screening (Day -28 to -1)	Baseline/Enrollment (Visit 1, Day 0)	(Visit 2, Day 1, POD 0)	(Visit 3, Day 2, POD 1+1)	(Visit 4, Day 3, POD 2+2)	(Visit 5, Day 8, POD 7+2)
Informed Consent	X	X				
Review and verify of Inclusion/Exclusion Criteria	X	X				
Demographics 	X					
Medical history and medication history	X					
Randomization and administer study intervention ketamine single-dose infusion or placebo			X			
Participants will be asked which treatment arm she believes she has been assigned				X		
Brief Pain Inventory (BPI)		X	X 	X	X	X
PROMIS sleep disturbance		X				X
PROMIS fatigue		X		X	X	X
Breast cancer pain questionnaire (BCPQ)						X
Opioid use and dosage assessment (medical records) and subject reports			X	X	X	X
Assessment of Adverse Events			X	X	X	X
Quality of Recovery (QoR-15)					X	X
Patient Health Questionnaire-2 (PHQ-2)		X				X
Generalized Anxiety Disorder-2 (GAD-2)		X				X
Side Effects (Psycho-Behavioral Questionnaire)			X	X		

Demographics should be collected, includes: age/ date of birth, race, MRN, gender, ethnicity, participant enrollment location, zip code, and disease site.

Only the pain severity subscale.

CONFIDENTIAL

This material is the property of the NYU School of Medicine and Langone Medical Center. Do not disclose or use except as authorized in writing by the study sponsor

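### Extra covariates in the BPI 24 h/48 h repeated-measures model and the adjusted secondary models are chosen by observed baseline imbalance, under a clinical criterion that is never defined

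*Combined protocol and SAP*

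**What the plan says.** Section 10.1 compares baseline characteristics between arms, using the Wilcoxon rank-sum test for continuous variables and Fisher's exact test for categorical ones. It then states: "The baseline balance will be determined by following both statistical and clinical significance criterion, with the latter as the primary".

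The result feeds three models:

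- **MMRM for BPI pain at 24 h and 48 h.** Baseline pain, treatment, time and their interaction are fixed. Then: "Unbalanced baseline variables will also be included".
- **Linear regressions for single-occasion secondary outcomes.** These estimate the treatment effect "while controlling for their preoperative value and unbalanced baseline variables".
- **MMRMs for repeated secondary outcomes** ("such as BPI, opioid use and fatigue scales at 1+1, 2+2, and 7+2 days after surgery"). "The MMRM model will include factors for treatment, time, treatment-by-time interaction, their preoperative values and unbalanced baseline variables".

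The only significance threshold is the general one in Section 10: "A two-sided p-value<0.05 will be considered statistically significant". Candidate variables are loosely bounded. The footnote to Section 19 reads: "Demographics should be collected, includes: age/ date of birth, race, MRN, gender, ethnicity, participant enrollment location, zip code, and disease site". Section 6.1.1 adds, for the baseline visit: "Subjects will complete the questionnaire packet for baseline assessments which will include BPI, PROMIS sleep disturbance, PROMIS fatigue, PHQ-2, and GAD-2". The medical and medication history taken at screening has no such bound.

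The primary endpoints are also compared by an unadjusted Wilcoxon test, and the sample size statement (Section 9.1.1) rests on that test.

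**The concern.** The clinical criterion outranks the statistical one but has no threshold, and no decision-maker or timing is named for it. The text also leaves open how the two halves combine. If both must be met, p<0.05 caps what can enter. If clinical judgement can override the test, nothing does. Two competent analysts could follow the plan on the same data and report different adjusted differences at 24 h and 48 h.

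A mechanical rule would still select on the wrong property. Allocation is by random permuted blocks (Section 9.2.1), so any imbalance is chance. A covariate improves precision when it predicts the outcome, and a between-arm test at baseline carries no information about that. A variable that is unbalanced but not prognostic is collinear with treatment and widens the standard error.

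A smaller point concerns the preoperative-value term in the secondary models. QoR-15 is collected only at POD 2 and 7 and BCPQ only at POD 7 (Sections 3.2.2 and 19), and neither is in the baseline packet. Opioid use is named as an MMRM outcome but is assessed only from PACU/POD 0 onward, and no preoperative opioid variable is defined.

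**Working it through.** **1. The plan's own figure.** Section 9.1.1 gives 80% power for a standardized effect of 1.1 with 15 per arm, two-sided alpha 0.05, Wilcoxon test, normal data. Simulating that test (40,000 runs) gives 79.7%. The figure reproduces and is not in dispute.

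**2. How often the p<0.05 half adds a covariate.** Baseline BPI pain is already in the primary model. I took ten further candidates from Sections 6.1.1 and 19:

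- six continuous: age, BPI interference, PROMIS sleep, PROMIS fatigue, PHQ-2, GAD-2;
- four treated as binary: race, ethnicity, location, disease site.

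Exact test sizes at 15 v 15 are 4.53% for the Wilcoxon test and f = 0.5% to 1.7% for Fisher's test (prevalence 0.1 to 0.5). For independent candidates:

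- P(any flag) = 1 - (1 - 0.0453)^6 × (1 - f)^4 = 0.258 (f = 0.005) to 0.293 (f = 0.017);
- if all ten were continuous: 1 - (1 - 0.0453)^10 = 0.371.

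**3. What a flag means.** By t-test with 28 df, the smallest flagged gap is 2.048 × sqrt(2/15) = 0.748 SD. At that threshold the squared correlation of covariate with treatment is 2.048²/(2.048² + 28) = 0.130. A non-prognostic covariate therefore widens the standard error by a factor of 1/sqrt(1 - 0.130) = 1.07, and by more for a larger gap.

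**4. Effect on the MMRM.** Simulation of the two-time-point model: REML, unstructured covariance, df 27 minus the number of covariates added, 6,000 runs in each of 12 cells. Assumptions: no missing data; 24 h-48 h correlation 0.6; baseline pain correlated 0.3 or 0.5 with outcome; zero, one or two candidates correlated 0.3 with outcome; continuous candidates correlated 0 or 0.5 with each other. Effect 1.1 is the plan's; 0.8 is added for range.

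| Quantity | Effect 1.1 | Effect 0.8 |
|---|---|---|
| Power, baseline BPI pain only | 84.3-91.9% | 57.9-68.3% |
| Power, with flagged covariates | 82.5-91.1% | 56.3-66.9% |
| Within-cell power loss (points) | 0.3-2.4 | 0.9-2.6 |
| Significance verdict changed, one time point | 1.9-4.0% | 3.5-5.8% |
| Verdict changed, either time point | 3.3-6.3% | 6.3-9.2% |

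A covariate is flagged in 27.8-29.6% of trials (independent candidates) or 24.1-25.3% (correlated). When one enters, the standard error widens by a median 7-10% and the estimate moves by a median 0.09-0.18 SD. Type I error is 4.3-5.3%, against 4.5-5.5% with baseline pain only.

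**5. Sensitivity** (5,000 runs per cell). With the 24 h-48 h correlation at 0.4-0.8, the loss at effect 1.1 is 0.8-1.5 points. With one or two candidates at r = 0.5, the power change at 1.1 runs from a 1.2-point loss to a 1.1-point gain.

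**6. How far the missing clinical cut-off matters.** The plan gives none, so these are illustrations. With 15 per arm, one continuous variable shows a standardized difference above 0.25 by chance in 50% of trials and above 0.5 in 18%. With six independent variables, at least one exceeds those limits in 1 - 0.50^6 = 98% and 1 - 0.82^6 = 70% of trials, against 1 - (1 - 0.0453)^6 = 24% under p<0.05.

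**7. Preoperative values.** The baseline packet holds BPI, PROMIS sleep, PROMIS fatigue, PHQ-2 and GAD-2. The term therefore exists for those scales, does not exist for QoR-15 and BCPQ, and is undefined for opioid use.

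**The case against.** The strongest reply is that little depends on this. The unadjusted Wilcoxon comparisons at 24 h and 48 h and the 80% power statement are untouched. Section 9.1.1 calls the trial a pilot not powered for a hypothesized effect, and the most obvious covariate, baseline pain, is already fixed. Type I error is not inflated, and the power loss is at most 2.6 points in the main cells. All of this stands, and it limits the weight of the point.

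It can also be said that the simulation covers only the half of the rule that has a threshold, and that its inputs are assumptions. That is true too. The clinical half cannot be sized without a cut-off. The candidate set is a guess: it omits extent of surgery (node dissection, unilateral or bilateral; Section 4.1), which a clinician might well raise. With strongly prognostic candidates the rule can gain a little power.

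Section 10.1 ties selection to baseline balance, so it does not license choosing a model by its result. I make no claim of inflated error on that ground.

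On the minor point, QoR-15 and BCPQ are not named in the model sentences and fall under them only by their visit schedule. An analyst would probably drop the missing term.

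None of this supplies the missing definition or makes observed imbalance a good basis for choosing covariates.

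**Conclusion.** The concern holds. The adjusted analyses of the primary endpoints, and the adjusted secondary analyses, rest on a covariate set settled after baseline data are seen, by a criterion the plan ranks first and does not define.

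In size it is a modest defect. For the p<0.05 half, under the assumptions in the working, roughly a quarter to 30% of trials would gain a covariate. The usual result is a small loss of power, with the verdict at one time point changed in 2-6% of trials when there is an effect. Step 6 shows that a looser clinical reading could change the model far more often, though its effect on power is not quantified. The plan should be changed on this point. The unadjusted tests do not depend on it. The preoperative-value mismatch affects only supplementary secondary models.

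**What to change.** In Section 10.1:

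- Remove unbalanced baseline variables from all three model sentences.
- Fix the covariate as the outcome's own preoperative value where one is collected: baseline BPI pain for the primary MMRM, and the same-scale baseline score for the secondary BPI, PROMIS fatigue, PROMIS sleep, PHQ-2 and GAD-2 models.
- By default add nothing further. If another covariate is wanted, name one on prognostic grounds before any data are examined by arm.
- Report any adjustment for a chance imbalance only as a labelled sensitivity analysis.
- Drop the preoperative term for QoR-15 and BCPQ. For opioid use, either define it from the screening medication history or drop it.
- Optionally, remove the significance tests from the baseline table.

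The cost is SAP wording only, with no new data or visits. The drawback is that the main model will not adjust for a chance imbalance outside the fixed set. Under the same assumptions, naming one further covariate costs 0.6-1.2 points of power at effect 1.1 (1.1-1.8 at 0.8) if it is not prognostic, and gains 2.1-2.8 points (2.1-4.9 at 0.8) if it correlates 0.3 with outcome.
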